6.2.1.5 Additional analysis of primary efficacy variables

Adjusted primary analysis of primary efficacy variables specified in section 6.2.1.2 (dose-response test) will be performed in PPS LVEF and PPS BNP respectively. Baseline values of atrial fibrillation, eGFR (≤ 60 mL/min/1.73m², >60 mL/min/1.73m²), gender, age group (<50 , 50-75 and >75), and BMI > 30 kg/m² will be used as covariates. In exploratory manner, the absolute change in LVEF (%) from baseline to week 20 will be categorized into four groups (≤ -5 , > -5 to <5 , 5 to <10 , ≥ 10). The number (%) of patients in each category of LVEF will be displayed by treatment group and overall. For further details including further categorization see the TLF Specification document.

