10.3.2 Statistical and analytical plans

All data will be listed and all variables will be summarized by means of descriptive statistics according to their type.

Summaries by treatment group using appropriate descriptive statistics will be provided for all study variables including demographic and baseline characteristics. Summary statistics will be presented for the original data as well as for the difference to baseline. Descriptive statistics such as arithmetic mean (or geometric mean, if applicable), median, standard deviation, quantiles, minimum, and maximum will be used to summarize continuous variables. Counts and percentages will be used to summarize categorical variables. Life tables and Kaplan-Meier estimates will be used to summarize time-to-event variables. Graphical data displays may also be used to summarize the data. Confidence intervals will be provided at a 2-sided level of 90% unless otherwise stated.

For this combined proof-of-concept and dose-finding study, an overall one-sided type I error level of 5% is planned to be used. The type I error will be controlled for the primary analysis of the primary variables.

There will be no formal control of the type I error for secondary or explorative analyses of the primary variables and any analysis of other efficacy variables.

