10.4 Determination of sample size

In the first step, this combined proof-of-concept and Phase IIb dose-finding study has been powered for the detection of a dose response signal in the primary efficacy variable change in LVEF.

The sample size for the primary efficacy variable change in LVEF was evaluated under the assumptions described in Section 10.3.2.2 and a type I error level = 5% with the aim to achieve at least 80% power for the one-sided primary multiple contrast test. The overall randomization ratio was assumed to be 3:1:2:2:2:2 for doses 0, 5, 10, 20, 30, and 40 mg.

Table 10–2 displays the power for the multiple contrast test in the MCP-Mod approach, used as primary analysis, for the set of specified alternatives.

Table 10–2: Power for multiple contrast test for set of different alternatives

Sample size		Power for alternative based on respective dose-response model (in %)					
Overall	Per group ^a	Linear	Sigmoidal E _{max} 1	Sigmoidal E _{max} 2	E _{max}	Quadratic	Minimum
240	40	73.36	86.24	81.20	82.26	79.97	73.36
252	42	75.26	87.73	82.94	83.94	81.70	75.26
264	44	77.10	89.13	84.58	85.58	83.31	77.10
276	46	78.71	90.30	85.97	86.94	84.70	78.71
288	48	80.31	91.39	87.30	88.25	86.09	80.31
300	50	81.62	92.27	88.42	89.32	87.24	81.62
312	52	82.99	93.15	89.53	90.38	88.39	82.99
324	54	84.25	93.92	90.54	91.37	89.50	84.25
336	56	85.43	94.60	91.45	92.22	90.39	85.43
348	58	86.56	95.22	92.31	93.02	91.28	86.56

^a Number of patients randomized to dose levels 10 mg, 20 mg, 30 mg, and 40 mg of neladenoson bialanate, for placebo sample size per group to be multiplied by 3/2, for dose level 5 mg sample size per group to be divided by 2.

To achieve at least 80% power for the multiple contrast test in the MCP-Mod approach under all different alternatives, a minimum of 48 patients per treatment group (72 patients for the placebo and 24 patients for the 5 mg group) is needed, resulting in an overall sample size of N = 288 patients.

In the second step, the power for the multiple contrast test in the MCP-Mod approach for the absolute change in log-transformed NT-proBNP was estimated, based on the assumptions outlined in Section 10.3.2.2 and a given sample size of $N = 288$. Statistical simulations were used to assess the power of the Hochberg test to reject at least one of the two null hypotheses. It was concluded that an overall sample size of $N = 288$ patients is sufficient to reject at least one of the two primary efficacy hypotheses with a power of about 83%.

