6.1.2 Demographic and Baseline Characteristics

Descriptive summaries of demographics and baseline characteristics will be presented by treatment group and overall for the PPS LVEF, PPS BNP, FAS and SAF populations. Comparability of the treatment groups with respect to demographics and baseline characteristics will be assessed using the descriptive summaries. Same analyses will also be performed for subjects who prematurely discontinue study participation or intake of study medication.

The following demographic data will be summarized:

- Age at baseline (years);
- Age category: <65, 65-75, >75 years;
- Gender (male vs. female)
- Race and ethnicity;
- Height (cm);
- Weight (kg) at baseline;
- BMI (kg/m²);
- BMI category: ≤30 vs. >30 kg/m²;
- Tobacco smoking history
- Alcohol consumption history
- Recent caffeine-containing beverage and chocolate consumption history

The following baseline characteristics will be summarized:

- LVEF(%) at baseline: ≤ 25 vs. > 25
- LVEF(%) at baseline: ≤ 40 vs. > 40
- LVEF(%) at baseline: ≤ 45 vs. > 45
- LVEF(%) at baseline: \leq mean vs. $>$ mean
- NT-proBNP (pg/ml) at baseline: \leq median vs. $>$ median
- NYHA class at baseline: II vs. III / IV
- Prior β -blocker: yes vs. no
- Region: North America / West Europe / East Europe / Asia
- Region: Japan vs. rest-of-the-world (analysis to be included in reports specific for Japan only)
- Time of CHF diagnosis to randomization (months): ≤ 3 vs. > 3
- Prior hospitalization for heart failure: yes vs. no
- Etiology of CHF: ischemic vs. non-ischemic
- Diabetes: yes vs. no
- Atrial fibrillation: yes vs. no
- Hypertension: yes vs. no
- Prior CHF medication:
 - Prior β -blocker in max tolerated dose: yes vs. no
 - Prior use of ivabradine: yes vs. no
 - Prior use of MRA: yes vs. no
 - Prior use of ACE inhibitor: yes vs. no
 - Prior use of ARB: yes vs. no
 - Prior use of angiotensin receptor-neprilysin inhibitor (ARNI): yes vs. no
- Estimated GFR (ml/min/1.73 m²): ≤ 60 vs. > 60

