Two primary variables have been defined to better evaluate multiple dimensions of the treatment effect, thereby adding a source of multiplicity. The overall outcome of the primary efficacy analysis will be considered positive if at least one of the two null hypotheses related to the primary efficacy variables can be rejected. The Hochberg (step-up) procedure will be applied to control the family-wise error rate (FWER):

Consider the null hypotheses for LVEF, $H_{0,LVEF}$, and for NT-proBNP, $H_{0,NT-proBNP}$, and their associated raw p-values p_{LVEF} and $p_{NT-proBNP}$. The Hochberg test is performed using the following steps:

1. If $\max(p_{LVEF}, p_{NT-proBNP}) \leq \alpha = 0.05$, both null hypotheses $H_{0,LVEF}$ and $H_{0,NT-proBNP}$ will be rejected and the procedure stops.
2. If $\max(p_{LVEF}, p_{NT-proBNP}) > \alpha = 0.05$ and $\min(p_{LVEF}, p_{NT-proBNP}) \leq \alpha/2 = 0.025$, we will fail to reject the null hypothesis related to the larger p-value $\max(p_{LVEF}, p_{NT-proBNP})$ and the null hypothesis related to the smaller p-value $\min(p_{LVEF}, p_{NT-proBNP})$ will be rejected.
3. Otherwise, we will fail to reject both null hypotheses $H_{0,LVEF}$ and $H_{0,NT-proBNP}$.

Assumptions

Five active doses of neladenoson bialanate will be used in this study: 5 mg, 10 mg, 20 mg, 30 mg, and 40 mg, as well as a placebo arm corresponding to a 0 mg dose.

The measurements of the primary efficacy variables are assumed to be normally distributed with the same standard deviation σ and independent between patients, respectively.

LVEF: The following assumptions were made for the absolute change from baseline in LVEF over 20 weeks:

- the expected mean effect under the placebo dose is conservatively assumed as an absolute increase from baseline of up to $\Delta = 2\%$ with a standard deviation of $\sigma = 7\%$
- while the maximum observable mean effect under neladenoson bialanate within the dose range considered is assumed as an absolute increase of $\Delta = 5\%$ with a standard deviation of $\sigma = 7\%$.

This results in an expected maximum effect size of $(5-2)/7 = 3/7 = 0.43$ under conservative assumptions. Note that the threshold of clinical relevance is an absolute difference of 3% in the change from baseline over the placebo control group.

NT-proBNP: The following assumptions were made for the absolute change from baseline in the log-transformed NT-proBNP over 20 weeks:

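### The SAP's only covariate-adjusted dose-response test enters age, eGFR and BMI as groups, with age bands used nowhere else in the plan: a small, avoidable loss of precision in an additional analysis

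*SAP*

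**What the plan says.** The primary test statistic in SAP 6.2.1.2 is built from unadjusted arm means. SAP 6.2.1.5 adds one adjusted version: "Adjusted primary analysis of primary efficacy variables specified in section 6.2.1.2 (dose-response test) will be performed in PPS LVEF and PPS BNP respectively". Its covariate list begins "Baseline values of atrial fibrillation, eGFR" (two groups, at or below 60 and above 60), continues "gender, age group (<50 , 50-75 and >75") and ends with BMI above 30 kg/m². Age, eGFR and BMI therefore all enter as groups. Atrial fibrillation and gender are binary by nature.

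Elsewhere age is banded differently. The baseline table in SAP 6.1.2 has "Age category: <65, 65-75, >75 years", and Protocol 10.3.2.1 lists the same bands for subgroups. SAP 4.5.4 takes its exploratory subgroups from 6.1.2. The bands below 50 and 50-75 occur only in 6.2.1.5. No reason is given there or in the SAP's document history. The eGFR cut at 60 and the BMI cut at 30 are the ones used in SAP 6.1.2 and Protocol 10.3.2.1.

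The protocol describes no covariate-adjusted dose-response test. On analyses of this kind, Protocol 10.3.2 states: "There will be no formal control of the type I error for secondary or explorative analyses of the primary variables".

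**The concern.** An adjusted test is there to show that the dose-response result stands once patient mix is taken into account, and to do so with as much precision as the covariates allow. Grouping a continuous covariate leaves the differences within each band unadjusted and returns part of the explained variance to the residual.

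The data do not force this. Protocol 9.3.1 records age, height and weight, with BMI calculated automatically. Protocol 9.6.3.1 has creatinine measured by the central laboratory, and Appendix 16.1 gives the eGFR formula.

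Adjustment has some work to do here. The per-protocol sets are selected after randomization and analysed as treated, and only about 75% of randomized patients are expected to contribute complete data (Protocol 10.4). Balance on age, renal function and BMI is therefore not fully protected by randomization.

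The unmatched age bands add a reporting problem: the adjusted test will not line up with the age categories in the baseline table and the subgroup summaries.

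**Working it through.** **1. The plan's own figures.** Inputs from Protocol 10.3.2.2 and 10.4 and SAP 6.2.1.2:
- maximum LVEF difference 3 points and SD 7 ("This results in an expected maximum effect size of" 3/7 = 0.43);
- "an overall one-sided type I error level of 5% is planned to be used";
- allocation 72/24/48/48/48/48 (placebo, 5, 10, 20, 30, 40 mg), N = 288.

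With contrasts proportional to n_i(μ_i − μ̄) and a multivariate t distribution with 282 degrees of freedom, simulated power is 80.2 / 91.4 / 87.3 / 88.2 / 86.2% for the five shapes in table order. The stated values are 80.31 / 91.39 / 87.30 / 88.25 / 86.09%. The SAP Table 6-2 contrasts match to within 0.001, and 288/0.75 = 384. The plan's figures reproduce.

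**2. Assumptions.** The documents give no distribution for age, eGFR or BMI and no correlation with outcome. Assumed: normal covariates with linear effects; age mean 60-72, SD 9-13; eGFR mean 50-75, SD 15-25; BMI mean 26-31, SD 4-6; joint R² 2-20%. eGFR and BMI were also tried truncated at the eligibility limits (30 and 40) and skewed.

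**3. Information lost by grouping.** Loss = 1 − (between-group variance / total variance). For a normal covariate cut at standardized points, each band (a, b) with probability p contributes (φ(a) − φ(b))²/p to the retained share.

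- *Two groups, best case (cut at the mean):* retained = 2 × 0.3989²/0.5 = 0.637 = 2/π, so the loss is 36.3%. An off-centre cut loses more.
- *eGFR at 60:* 36-56% lost (33-56% when truncated at 30).
- *BMI at 30:* 36-56% lost (32-56% when truncated or skewed).
- *Age <50 / 50-75 / >75, mean 67, SD 11:* cuts at (50 − 67)/11 = −1.545 and (75 − 67)/11 = 0.727; band shares 0.061, 0.705, 0.234. Retained = 0.1209²/0.061 + (0.1209 − 0.3062)²/0.705 + 0.3062²/0.234 ≈ 0.69, so about 31% is lost. Over the whole grid the loss is 25-44%.
- *Age <65 / 65-75 / >75:* 22% lost at mean 67, SD 11, and 19-39% over the grid. The plan's usual bands are better in most cases but not all. At mean 60, SD 11-13, they lose 33-35%, against 25-31% for the bands in 6.2.1.5.

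**4. Effect on residual variance.** Ratio of grouped to continuous = (1 − R²(1 − loss))/(1 − R²). With a loss of 36% for the three together:

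| Joint R² | Calculation | Excess residual variance | Power, continuous | Power, grouped |
|---|---|---|---|---|
| 2% | 0.9872/0.98 | 0.7% | 80.9% | 80.7% |
| 5% | 0.968/0.95 | 1.9% | 82.0% | 81.3% |
| 10% | 0.936/0.90 | 4.0% | 83.8% | 82.5% |
| 20% | 0.872/0.80 | 9.0% | 87.5% | 84.9% |

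Power is for the linear shape, the weakest alternative, at N = 288, with SD 7√(1 − R²) for continuous terms and 7√(1 − 0.64R²) for grouped ones. Before rounding, the gap runs from about 0.3 to 2.7 points. A larger average loss would widen it: at 50% lost and R² = 20%, the ratio is (1 − 0.10)/0.80 = 1.125.

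**5. Weight of the 5 mg arm.** Each arm's share of the contrast variance is (c_i²/n_i)/Σ(c²/n). For the linear contrast, 0.159²/24 = 0.00105 against a total of 0.0182, or 5.8%. Across the five contrasts the 5 mg share is 5.8, 11.8, 8.5, 0.6 and 4.2%; the placebo share is 28-74%.

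**The case against.** The strongest reply is that no decision rests on this analysis. The sample size was set "with the aim to achieve at least 80% power for the one-sided primary multiple contrast test", which is unadjusted, and SAP 6.2.1.5 is an extra. That stands, and it sets the ceiling on the point's importance. The power points above only express the loss on a familiar scale; the adjusted test has no power target.

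A second reply is that assuming a linear effect guarantees that the continuous term wins, whereas with a threshold or curved effect bands can do as well or better. This also stands, so the sizes are conditional and linearity should be checked. Randomization cannot be relied on to make a wrong functional form harmless, because the analysis is run in the per-protocol sets.

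A third reply is that bands for tables and bands for a model serve different purposes. A reader might call the two sets of age bands a contradiction. The documents support only an unexplained difference. Nor do they support extending the inconsistency to eGFR or BMI, whose cuts match the rest of the plan.

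A reader might also infer that the harm falls mainly on the small 5 mg arm (about 24 evaluable patients). For a contrast test it does not, because that arm carries only 0.6-11.8% of the contrast variance.

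**Conclusion.** The point holds and is minor. The plan's one adjusted dose-response test groups three covariates that are available as continuous values, and its age bands have no counterpart or explanation elsewhere.

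Under assumed normal distributions and linear effects, about a third to a half of the linear information in eGFR and BMI is lost (32-56% in the cases tried), and about a quarter to two-fifths of that in age (25-44%). It would be tempting to say that a third or more is lost for all three. For age this is not assured: at an SD of about 11 or more the loss is below a third.

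At joint R² of 2-20% and a 36% loss, residual variance is about 1-9% larger than it need be, or roughly 0.3-2.7 power points. The primary result and its error control are untouched.

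**What to change.** In SAP 6.2.1.5, enter age (years), eGFR (mL/min/1.73 m²) and BMI (kg/m²) as continuous covariates, with atrial fibrillation and gender as factors. Add a sentence that the linearity of the three terms will be checked. If age bands are kept, use those of SAP 6.1.2 or state why others are preferred.

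The cost is a wording change and one model statement, and no new data are needed. The model uses one fewer degree of freedom, since a single age slope replaces two age-group terms. The small downside is the assumed linear effect. It needs the check because the per-protocol sets do not keep the full protection of randomization.

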6.2.2 Secondary efficacy variables and analyses

6.2.2.1 Secondary efficacy variables

Secondary efficacy variables across different domains are:

- Key echocardiographic parameters, measured values and absolute change from baseline at 20 weeks:
 - Left ventricular end-systolic volume (LVESV; mL)
 - Left ventricular end-diastolic volume (LVEDV; mL)
- High sensitivity troponin T (hs-TNT; ng/L), measured values (log transformed) and absolute / relative change from baseline at 20 weeks as a biomarker of myocardial injury
- Time from randomization to clinical outcomes: CV mortality, HF hospitalization and urgent visits for HF (separate and composite)

6.2.2.2 Primary analyses of secondary efficacy variables

The primary analysis of key echocardiographic parameters will be performed in PPS LVEF and other secondary efficacy variables will be performed in PPS BNP. The missing values of post baseline of LVESV and LVEDV will be imputed by WOV if the baseline values are not missing and the subjects have CV death or HF hospitalization, otherwise remains missing. Similarly The missing values of post baseline of hs-TNT will be imputed by WOV if the baseline values are not missing and the subjects have CV death or HF hospitalization, otherwise remains missing. The secondary efficacy variables, except for the clinical outcomes, will be analyzed using similar statistical methods as for the primary efficacy

variables, i.e. the MCP-Mod method with the same standardized candidate dose-response shapes (with the proper direction: decreasing trend for change of LVESV, LVEDV and log-transformed hs-TNT) and corresponding coefficients as for the primary variables.

Time to adjudicated clinical outcome event since randomization (using both separate and composite outcomes) will be described by means of Kaplan-Meier (KM) estimates by treatment group. The subjects who do not have the corresponding clinical outcomes until week 26 visit (upper time limit, i.e. 182+7days) will be considered as right-censored at the minimum of date of last visit, date of week 26 visit, study day 189, and date of death (in case death is non CV death). KM estimates for each visit will be tabulated.

Additionally time to adjudicated on-treatment clinical outcome events since randomization (using both separate and composite outcomes) will also be described up to 6 weeks after last dose in each treatment arm respectively. The subjects who do not have the corresponding clinical outcomes until 6 weeks after last dose will be considered right censored at minimum of 6 weeks after last dose, date of last visit and date of death (in case death is non CV death).

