6.4 Withdrawal of patients from study

6.4.1 Withdrawal

This section was changed in Amendment 2, see Section 15.1 for details.

An excessive rate of withdrawals (either patients discontinuing study medication or study withdrawal) can render the study non-interpretable. Therefore, un-necessary withdrawal of patients should be avoided and all efforts should be taken to motivate patients to comply with all the study specific procedures and to be followed until the end of the trial to detect the occurrence of cardiovascular events / assess vital status.

Before permanently discontinuing study medication (either initiated by the patient or the investigator) an interruption should be considered. Patients, who have temporarily discontinued study medication for any reason, should restart as soon as medically justified in the opinion of the investigator; the patient can re-start at any time before the end of treatment

(EOT) visit. In addition, patients should not be withdrawn from the study drug or from the study solely due to reaching a potential cardiovascular event.

All patients who permanently discontinue study medication should come in for the EOT / premature discontinuation visit as soon as possible after discontinuation of the study medication and the safety follow-up visit 4 weeks after the last dose. In addition, they will be contacted by the investigator via the scheduled Week 26 phone call to assess occurrence of cardiovascular events.

The investigator should show due diligence and explore all possible options to reach a patient who fails to return to a visit. The site must document all attempts to try to contact the patient in the medical records / source documents.

In order to avoid loss-to-follow-up, the investigator should ask the patient at the study start for the contact details of a relative or friend who can be contacted in case the patient cannot be reached.

Patients should not be withdrawn from follow-up unless the patient explicitly withdraws consent to be contacted. All efforts should therefore be made to minimize the number of patients who withdraw such consent as, in general, no further information on cardiovascular events and survival status may be collected after that point.

Withdrawal criteria

Patients **must be withdrawn from the study** if any of the following occurs:

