9.2.10 Visit 9 (Week 26, phone call)

Twenty-six weeks after the start of study treatment the site personnel will call the patients to inquire about adverse events, including cardiovascular events, and to collect information on concomitant medications. For patients who discontinue study drug treatment early, the phone call will still be made 26 weeks after the start of study treatment. Information collected during the phone call must be recorded in the patient's medical records / source documents.

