11.4 Missing data

The following measures will be implemented to minimize the amount of missing data.

- Encourage further participation in the study, i.e. phone call 26 weeks after the start of treatment, even if the study medication is discontinued early.

- If the patient does not attend the visits in person, the investigator should make every effort to collect information on mortality and / or hospitalization from other sources, e.g. family / friend / general physician / etc.
- Ask sites to call patients the day before certain study visits to remind them to remember the time they take their study medication and to remind them in case study medication should not be taken at home the next day.
- Educate patients on the AVIVO device and train sites to prepare the patient's skin for adherence of the sensor. Ask sites to call patients at the end of the wearing period to provide instructions for removal, storage and return at the next visit.
- Try to avoid unnecessary patient withdrawals (see Section 6.4).

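### Clinical-outcome censoring: adjudicated events learned of after a patient's last visit count, but event-free time known for the same period is discarded

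*SAP*

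**What the plan says.** The secondary clinical outcomes are CV mortality, HF hospitalization and urgent visits for HF, separately and as a composite (SAP 6.2.2.1). SAP 6.2.2.2 describes them with Kaplan-Meier estimates by treatment group. The censoring rule applies to "The subjects who do not have the corresponding clinical outcomes until week 26 visit (upper time limit, i.e. 182+7days"), who are "right-censored at the minimum of date of last visit, date of week 26 visit, study day 189, and date of death", where the death is non-CV. The on-treatment analysis uses the same construction: "right censored at minimum of 6 weeks after last dose, date of last visit and date of death", again for non-CV death. The document history in SAP 7 says that version 3.0 added detail on the censoring of time-to-event variables, so this is the operative rule.

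Four other places bear on it:

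- Protocol 11.4: when patients do not attend in person, "the investigator should make every effort to collect information on mortality and / or hospitalization from other sources".
- Protocol 9.2.10: "For patients who discontinue study drug treatment early, the phone call will still be made 26 weeks after the start of study treatment". This call is numbered Visit 9.
- Protocol 6.4.1: once a patient withdraws consent to be contacted, in general "no further information on cardiovascular events and survival status may be collected after that point".
- SAP 6.2.2.2 makes PPS BNP the primary set for these outcomes. SAP 6.2.2.3 repeats the analysis in the FAS (to Week 26) and the SAF.

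Neither document stops event counting at the patient's own last visit, and neither defines a last date of known status.

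**The concern.** Two things follow from putting the last visit inside the minimum.

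First, the non-CV death term does almost nothing. The last visit comes before death, so the minimum picks the visit. A patient seen at Week 12 (day 84) who dies of a non-CV cause on day 139 is censored on day 84, although known to be at risk for another 55 days. The exception is a contact dated after death and recorded as a visit, such as a Week 26 call answered by a relative.

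Second, censoring depends on what happens later. Take two patients last seen on day 84, both followed up through a family physician. If the physician reports an HF hospitalization on day 150 and it is adjudicated, the patient stays in the risk set to day 150 and counts as an event. If the physician reports no event, the patient leaves on day 84. Kaplan-Meier estimation requires censoring to be unrelated to later outcome, and here it is not.

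These curves are part of the evidence on dose. Protocol 10.3.2.3 combines primary and secondary variables to judge the drug effect over dose levels, and SAP 6.2.1.2 lets other efficacy variables and safety influence the choice of target dose.

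**Working it through.** **The plan's own figure.** Upper time limit: 182 + 7 = day 189, as stated. The documents give no event rate and no share of patients lost to contact, so everything below rests on assumptions.

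**Closed-form check.** Assume a constant hazard, a true day-182 risk R, and a fraction p of patients with no visit after Week 12 (day 84). A share c of the later events in that fraction is learned of. Write S = 1 − R and A = S^(84/182), the event-free probability at day 84. After day 84 the risk set under the SAP rule holds

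- patients still attending: (1 − p)A
- non-attenders whose later event will be learned of: p·c·(A − S)

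Event-free patients remaining at day 182: (1 − p)S. Hence

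KM risk = 1 − A × (1 − p)S / [(1 − p)A + p·c·(A − S)]

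For R = 10%, A = 0.9^(84/182) = 0.9525. With p = 25% and c = 1, the denominator is 0.7144 + 0.0131 = 0.7275 and the numerator 0.675, so the risk is 1 − 0.9525 × 0.675/0.7275 = 11.6%. The other cells, for a true 10%:

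| Share affected | No later events learned of | Half | All |
|---|---|---|---|
| 5% | 10.0% | 10.1% | 10.3% |
| 10% | 10.0% | 10.3% | 10.5% |
| 25% | 10.0% | 10.8% | 11.6% |

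**Simulation with a different stopping pattern.** 400,000 patients per scenario, the protocol's contact schedule, uniform stopping times, 1% non-CV death by day 189, results read at day 182. With all later events learned of and equal risk in patients who stop, the SAP rule against the truth gives:

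| True day-182 risk, about | 5% stop | 10% stop | 25% stop |
|---|---|---|---|
| 5% | +0.15 | +0.3 | +0.85 |
| 10% | +0.3 | +0.6 | +1.6 |
| 20% | +0.5 | +1.0 | +2.9 |

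(percentage points). The death date set the censoring date in no patient in any scenario; post-death contacts were not simulated. With nobody stopping, so that only non-CV deaths are affected, the shift was about 0.01 points (9.64% against 9.63%).

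**Time lost per non-CV death.** Numbered contacts fall on days 0, 14, 28, 56, 84, 140, 168 and 182, giving gaps of 14, 14, 28, 28, 56, 28 and 14 days. For a death at a uniformly distributed time, the mean time since the last contact is 6,076/(2 × 182) = 16.7 days, with a maximum of 56. If the unnumbered Week 19 call (day 133) also counts as a visit, these become 5,390/364 = 14.8 and 49 days.

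**Consistent rules.** In the example with 25% stopping and all later events learned of (true day-182 risk 9.6%), the SAP rule gives 11.2%. Counting non-attenders' events only up to their last visit gives 9.7%. Censoring at the last date of known status gives 10.0% at day 189, against a true 10.0%.

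**The case against.** The strongest reply is about reach. The primary set for these outcomes is PPS BNP, which excludes patients whose post-baseline NT-proBNP is missing for reasons other than CV death or HF hospitalization (SAP 5.1). Most event-free non-attenders are therefore outside it. That stands: the figures above describe the FAS and SAF analyses better than the primary one. The selection built into PPS BNP can push risk up too, but through the set definition and not through this rule.

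The affected group is also narrow. Patients reached at Week 26 have Visit 9 as their last visit and lose nothing. Those who withdraw consent to contact in general yield no later events. The 25% in Protocol 10.4 is an allowance for drop-out and for invalid or missing data in the PPS; it is not a forecast of lost Week 26 contact, and it serves here only as an upper bound. Full capture is generous, because events must be adjudicated and Protocol 11.4 asks for best efforts without guaranteeing a result.

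A reader might infer that the reported risks must be too high. The documents do not support that. The rule's own effect is upward, but missed events pull the other way. If patients who stop have three times the hazard, 10% stop, and half of their later events are learned of, the simulated estimate is 11.0% against a true 11.2%.

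A reader might also infer that a poorly tolerated dose would show a visible false excess of events. Two arms with equal 10% risk and 5% versus 25% affected would differ by 11.62 − 10.26 = 1.4 points. With 64 patients per arm, the standard error of one arm's risk is √(0.1 × 0.9/64) = 3.8 points, and of a difference 5.3 points. Nothing in the documents points to such an imbalance.

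None of this makes the rule consistent. These points limit its size and leave the asymmetry in place.

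**Conclusion.** The concern holds as a defect of limited size in a stated derivation. Events and event-free follow-up from the same source are treated differently, and the non-CV death term is practically inert. To say it can never apply would go too far, because of the post-death contact described above. On Kaplan-Meier risk the rule itself acts upward. At a true 26-week risk of about 10% the excess runs from nil, when no later events are learned of, to about 0.3 points (5% affected) or 1.6 points (25%, an upper bound) when all are. These sizes rest on assumed event rates, affected shares and capture, on a constant hazard, and on equal risk in patients who stop attending. The total error in a reported estimate may have either sign. The outcomes are secondary and descriptive, with no test attached, so type I error and power are not touched. The change is still worth making before the curves inform the choice of dose.

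**What to change.** Apply one follow-up cut-off to events and censoring in SAP 6.2.2.2.

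- **Preferred.** Censor event-free patients at the earliest of the last date on which event status is known (visit, phone call or documented third-party information), study day 189, and death from a cause that is not the event analysed. Remove the last visit as a separate term.
- **If dates of last known status are not in the database.** Count events only up to the date at which the patient would otherwise be censored, accepting the date of death as a last-known date. Without that allowance, CV deaths falling between visits would be lost. Some asymmetry remains for deaths reported after attendance has stopped, so this is second best.

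Use the same rule in the on-treatment analysis, with 6 weeks after last dose as the limit.

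The cost is SAP wording and one changed derivation. The preferred option may also need last-contact dates retrieved from source records: Protocol 6.4.1 and 9.2.10 place contact attempts and call information in medical records or source documents, and neither document shows a field for them in the eCRF. It also works only if sites document event-free reports from third parties as carefully as events; otherwise part of the asymmetry returns.
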